9.2.1 Study Period

Study Period: From 6 months after blinatumomab launch date to when observation of all patients registered is completed (May 2019 to September 2023)

Enrollment Period: From 6 months after blinatumomab launch date to when the registration of the target number of subjects is completed (May 2019 to September 2022)

9.2.2 Selection and Number of Sites

About 250 nation-wide medical institutions equipped with department of Hematology, Medical Oncology, Pediatric Oncology, others and medical experts of committing participation and co-operation of the study.

9.2.3 Subject/Patient/Healthcare Professional Eligibility

9.2.3.1 Inclusion Criteria

Patients for whom blinatumomab is prescribed in the cycle 6 or later at medical institutions.

Approved

9.2.3.2 Exclusion Criteria

No exclusion criteria are applied.

9.2.4 Matching

No matching is used.

9.2.5 Baseline Period

Patient background at the start of cycle 1 blinatumomab administration will be collected as baseline data.

9.2.6 Study Follow-up

Each patient will be followed from the beginning of cycle 6 to the end of cycle 9.

If administration of blinatumomab will be stopped or terminated between the beginning of cycle 6 and the end of cycle 9, the safety follow-up period shall be 30 ± 3 days after the final administration or up to the day before the implementation of hematopoietic stem cell transplantation or other antitumor therapy.

9.3 Variables

Information described in Sections 9.3.1-9.3.3 is collected in case report form (CRF) per a patient. CTCAE grade ≥ 3 or higher adverse event and other safety information are collected throughout the follow-up period.

9.3.1 Exposure Assessment

Daily dosage, period and reason for change/termination of blinatumomab are collected in CRF.

9.3.2 Outcome Assessment

CTCAE grade ≥ 3 or higher adverse events (including grade, seriousness and causal relations to drug) during the observational period or safety follow-up period are collected by using CRF and applicable safety reporting form. If adverse events or serious adverse events are due to the primary disease, all signs and symptoms obtained are reported. Mortality due to disease progression when information on symptoms and symptoms cannot be obtained is reported as the primary tumor (e.g. relapsed or refractory B-cell ALL).

9.3.3 Covariate Assessment

Following data are collected in patient registration form and CRF.

Approved

Patient information for registration: patient ID, sex, birth year/month, continuation status from 20170655 study, date of informed, start date of cycle 6 blinatumomab administration

Patient demographics and medical history (in case the patient is not continuing from 20170655 study): pregnancy/lactation, medical history (including central nervous system lesion or symptom, hepatic dysfunction and renal dysfunction), therapeutic history before blinatumomab administration to B-cell ALL, history of hematopoietic stem cell transplantation, Philadelphia chromosome examination

Pregnancy and lactation during observation period: birth (planned) years/month

Concomitant medication (excluding complication treatment medicine and CTCAE grade ≤ 2 adverse event treatment medicine): medicine name, duration, dosage

Concomitant therapy to primary disease: therapy name, duration

9.3.4 Validity and Reliability

It is a prospective, observational cohort study, so variables, which can be measured at medical sites in the real-world medical practice, are selected for this survey in reference to prior blinatumomab clinical trials and advice from local medical experts.

Exposures, outcomes, and all other variables observed and measured by each medical site will be collected through paper CRF and entered into a database constructed by the external service provider, EPS Corporation, Tokyo, Japan. Standardized error check program will be constructed in the data management system. If a logical discrepancy in CRF and clear error is identified, a query form will be prepared and delivered to the institutional site physicians for clarification and correction. Site physicians and staff are requested to check the data against medical records, and accuracy and completeness of data consistent with information in medical records is confirmed and attested by signature of investigators.

9.4 Data Sources

The original source of the data used in the survey is patient medical records. Data are collected through CRF, which are populated by the investigators.

Laboratory test values will be measured by each medical site with their own method.

9.5 Study Size

The targeted number of patients was set to 40 subjects to enable a consistent comparison and discussion on the safety during the maintenance phase in Japanese

patients and blinatumomab clinical trial (00103311 study) by collecting the information from the similar number of subjects as 36 subjects who underwent maintenance therapy of blinatumomab in 00103311 study. The incidence of CTCAE grade ≥ 3 neurologic events, infections and myelosuppression between cycles 6 and 9 in 00103311 study was 8.3% (3/36), 22.2% (8/36) and 16.7% (6/36) respectively. The collection of 40 subjects who transition to cycle 6 enables that the events with a true incidence of 8% or above are collected from at least 1 subject with 95% confidence, and thus a consistent evaluation for CTCAE grade ≥ 3 neurologic events, infections and myelosuppression is considered possible.

9.6 Data Management

Data are collected by paper CRF.

Data management is conducted by EPS Corporation under its own standard operating procedure with oversight by the Amgen Astellas BioPharma K.K.

9.6.1 Obtaining Data Files

Not applicable

9.6.2 Linking Data Files

Not applicable

9.6.3 Review and Verification of Data Quality

Quality and completeness will be annually confirmed by self-inspection per the local good post-marketing study practice (GPSP).

9.7 Data Analysis

Patient disposition, demographics and baseline characteristics will be summarized. The number of patients and the incidence rates of CTCAE grade ≥ 3 events are tabulated for each safety specifications and other adverse drug reactions during the survey. Statistical test (chi-square, etc.) will be applied, depending on the type of variable (nominal, ordinal, etc.). Imputation for missing data will be considered if it is possible and empirically worth to do imputation of missing data. Statistical analysis will be conducted by EPS Corporations in accordance with the Statistical Analysis Plan (SAP), provided by Amgen Astellas BioPharma K.K.

9.7.1 Planned Analyses

For the timely sharing of the collected data with PMDA and Health care professionals (HCPs), analysis of interim data will be performed at the timing of Japan periodic safety update report (J-PSUR). After the last patient enrolled to meet the expected sample size

completes the observational period, a data analysis will be performed and a final report summarizing the results of the survey will be completed shortly thereafter. For final analyses, the local external medical experts will review the survey analysis results.

9.7.1.1 Primary Analysis

The primary analysis will be conducted after all the survey data are collected and cleaned.

Patient disposition, demographics and baseline characteristics will be summarized. Statistical test (chi-square, etc.) will be applied, depending on the type of variable (nominal, ordinal, etc.). See Sections 9.7.2.4 and 9.7.3 for analyses planned to address specified endpoints.

9.7.2 Planned Method of Analysis

9.7.2.1 General Considerations

In general, a descriptive analysis is conducted. Categorical variables are summarized with frequencies and percentage. Continuous variables are summarized with mean, standard deviation (SD), median, 1st Quartile (Q), and 3rd Q. When statistical testing and inference are applied, two-sided p-value of <0.05 is considered significant and the 95% CI is estimated. Adjustment for multiple comparisons is not considered.

[figure not shown]
9.7.2.2 Missing or Incomplete Data and Lost to Follow-up

Participating investigators (physicians) and co-medicals are requested to make an effort to provide as complete information as possible through CRF. It is assumed that blinatumomab prescriptions would typically be started and patients observed at hospitals with experts of oncology. The rate of lost to follow-up is estimated to be close to 0% as possible. Imputation for missing data will be considered if it is possible and empirically worth to do imputation of missing data.

[figure not shown]
9.7.2.3 Descriptive Analysis

9.7.2.3.1 Description of Study Enrollment

All enrolled patients will be summarized in the tree of patient disposition, as described below:

Approved

Percentage of a% and b% (corresponding to enrollment) will be calculated.

9.7.2.3.2 Description of Subject/Patient Characteristics

Patient characteristics will be summarized for the following variables.

Patients demographic: sex, birth year/month, reason for usage, experience of usage, pregnancy/lactation, medical history (including central nervous system lesion or symptom, hepatic dysfunction and renal dysfunction), therapeutic history before blinatumomab administration to B-cell ALL, history of hematopoietic stem cell transplantation, Philadelphia chromosome examination, pregnancy and lactation during observation period, concomitant medication, concomitant therapy to primary disease

9.7.2.4 Analysis of the Primary, Secondary, and Exploratory Endpoint(s)

Analysis for specified endpoints will be conducted as follows:

- Primary endpoint for safety:

The number of patients and the incidence rates of CTCAE grade ≥ 3 events are tabulated for each safety specifications and other adverse drug reactions during the survey (see Section 11.1 the definition of adverse event, serious adverse event, and other safety findings to be collected).

9.7.2.5 Sensitivity Analysis

9.7.2.5.1 Subgroup Analysis

If necessary, summarize the number of patients and the incidence rates of each safety specifications and all adverse drug reactions for each patient background, such as adults and pediatric.

9.7.2.5.2 Stratified Analysis

Stratified analysis will be conducted by covariates as below:

- Patient demographics (e.g., age group, preexisting disease etc.)
- Medication status (e.g., dosage and duration of blinatumomab therapy, concomitant medication for ALL)

9.7.2.5.3 Sensitivity Analysis for Residual Confounding and Bias

No sensitivity analysis is pre-planned.

9.7.2.5.4 Other Sensitivity Analysis

No sensitivity analysis is pre-planned.

Approved

9.7.3 Analysis of Safety Endpoint(s)/Outcome(s)

See Section 9.7.2.4.

9.8 Quality Control

Quality control is conducted by checking whether data management operations were conducted based on the standard operation procedures of data management, and all results of quality control, including deviations and their measurements, are documented/reported and corrected deviations appropriately if they were found.

9.9 Limitations of the Research Methods

This is a prospective, observational cohort study, so it has a limitation of internal validity and strength of external validity in comparison with an interventional clinical study. Limitations common to this type of study, along with how to reduce errors, are summarized below.

Limitations	How to reduce errors
Missing and incomplete data are unavoidable, because there are some cases that data could not be collected at all evaluation time points, and some patients could be lost to follow-up.	Efforts will be made to collect as complete data as possible and instructions to investigators. After examining the extent of missingness and incompleteness of study data, an appropriate statistical data imputation method will be considered if it is possible and empirically worth to do imputation of missing data.
Selection bias, information bias and confounding cannot be excluded.	Selection of participating medical institutions nationwide and enrollment of all patients who will receive blinatumomab prescriptions in the cycle 6 or later at the eligible institutions as much as possible during enrollment period without exclusion criteria. Analysis results will be interpreted with caution, acknowledging the limitations, whether or not appropriate statistical methods could be applied to address the bias.

10. Protection of Human Subjects

The study protocol is reviewed and approved by the local regulatory agency, PMDA as well as external ethical committee (EC). The study and data collection are conducted in accordance with the Pharmaceutical and Medical Device Act, GPSP and Helsinki Declaration. Local Medical Act provides the physician and co-medical 'Confidentiality Obligation' of patients that is set forth in the study agreement between the representatives of study site and Amgen Astellas BioPharma K.K.

Before registering the patient to this study, physician informed the patient about the aim, method, and potential risk of the study and utilization of the patient's data in keeping individual patient's information unidentified.

11. Collection, Recording, and Reporting of Safety Information and Product Complaints

The external vendor, EPS Corporation, in charge of day-to-day survey operation will check incoming safety information (adverse events, use in pregnant/lactating women) on data management system and CRF daily, and report the information to the Safety Department at Amgen Astellas BioPharma K.K. in accordance with standard operating procedures of Amgen Astellas BioPharma K.K.

11.1 Definition of Safety Events

11.1.1 Adverse Events

An adverse event is any untoward medical occurrence in a patient administered a pharmaceutical product(s) irrespective of a causal relationship with this treatment.

An adverse event can therefore be any unfavorable and unintended sign (including an abnormal laboratory finding, for example), symptom, or disease temporally associated with the use of a product(s), whether or not considered related to the product(s). The definition of an adverse event includes:

- Worsening of a pre-existing condition or underlying disease
- Events associated with the discontinuation of the use of a product(s), (eg, appearance of new symptoms)

It is the investigator's responsibility to evaluate whether an adverse event is related to an Amgen Astellas BioPharma K.K. product prior to reporting the adverse event to Amgen Astellas BioPharma K.K.

11.1.2 Serious Adverse Events

A serious adverse event is any adverse event as defined above that meets at least one of the following serious criteria:

- is fatal
- is life threatening (places the patient at immediate risk of death)
- requires in-patient hospitalization or prolongation of existing hospitalization
- results in persistent or significant disability/incapacity
- is a congenital anomaly/birth defect
- is an "other medically important serious event" that does not meet any of the above criteria

Approved

A hospitalization meeting the regulatory definition for “serious” is any in-patient hospital admission that includes a minimum of an overnight stay in a healthcare facility.

“Other medically important serious events” refer to important medical events that may not be immediately life threatening or result in death or hospitalization but may jeopardize the patient or may require intervention to prevent one of the other outcomes listed in the definition above. Examples of such events could include allergic bronchospasm, convulsions, and blood dyscrasias, drug-induced liver injury, events that necessitate an emergency room visit, outpatient surgery, or other events that require other urgent intervention.

11.1.3 Other Safety Findings

Other Safety Findings (regardless of association with an adverse event) include:

- Medication errors, overdose, whether accidental or intentional, misuse, or abuse involving an Amgen product,
- Pregnancy and lactation exposure,
- Transmission of infectious agents,
- Reports of uses outside the terms for authorized use of the product including off-label use,
- Occupational exposure,
- Any lack or loss of intended effect of the product(s).

11.1.4 Product Complaints

Product Complaints include any written, electronic, or oral communication that alleges deficiencies related to the identity, quality, durability, reliability, safety, effectiveness, or performance of a product or device after it is released for distribution to market or clinic by either Amgen Astellas BioPharma K.K. or by distributors and partners for whom Amgen Astellas BioPharma K.K. manufactures the material. This includes any drug(s), device(s) or combination products provisioned and/or repackaged/modified by Amgen Astellas BioPharma K.K. Drug(s) or device(s) includes investigational product.

Product complaints are collected separately from this survey in accordance with standard operating procedures of product complaints of Amgen Astellas BioPharma K.K.

11.2 Safety Collection, Recording and Submission to Amgen Requirements

This study is collecting information from investigators prospectively at a point in survey. All safety events (adverse events, product complaints, and other safety findings) considered to have occurred following patient exposure to blinatumomab will be

collected during observational study period from start of cycle 6 administration to final study contact with the exception of the protocol-exempted events listed below. The investigator is responsible for recording safety events that they become aware of during study period in the patient's appropriate study documentation. Collected safety events must be submitted as individual safety reports to Amgen Astellas BioPharma K.K. via the Safety Reporting Form (paper form) provided by the Safety Department of Amgen Astellas BioPharma K.K. promptly.

Protocol Exempted Events

CTCAE grade ≤ 2 events are not required to be individually reported or collected in the study. If any of the exempted events have a fatal outcome, they should be considered a serious adverse event and must be collected and reported individually to Amgen Astellas BioPharma K.K. promptly. All safety information that is not specified in this section is to be collected and submitted to Amgen Astellas BioPharma K.K. promptly. Protocol-exempted events and safety events that are suspected to be related to any medicinal product other than Blinatumomab should be reported to the local authority in line with the local country requirements.

See [Appendix C](#) for sample Safety Report Form(s) and [Appendix E](#) for sample Pregnancy and Lactation Notification Worksheets. The Investigator may be asked to provide additional information for any event submitted, which may include a discharge summary or extracts from the medical record. Information provided about the event must be consistent with information recorded in the study documentation where safety data may also be recorded.

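### The reporting exemption in Section 11.2 is set by CTCAE grade alone, so non-fatal serious events of grade 2 or lower need not enter the survey or reach the sponsor

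*Protocol*

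**What the plan says.** Protocol Section 11.2 requires collection of all safety events from the start of cycle 6 to the last study contact, apart from protocol-exempted events. The exempted class is defined in one sentence: "CTCAE grade ≤ 2 events are not required to be individually reported or collected in the study". One exception follows: "If any of the exempted events have a fatal outcome, they should be considered a serious adverse event and must be collected and reported individually". A residual clause then says: "All safety information that is not specified in this section is to be collected and submitted to Amgen Astellas BioPharma K.K. promptly". A further sentence gives another route: "Protocol-exempted events and safety events that are suspected to be related to any medicinal product other than Blinatumomab should be reported to the local authority". Local rules govern that reporting.

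Section 11.1.2 opens: "A serious adverse event is any adverse event as defined above that meets at least one of the following serious criteria". Six criteria follow: death, threat to life, hospitalization, disability, congenital anomaly, and other medically important events. The hospitalization criterion reads "requires in-patient hospitalization or prolongation of existing hospitalization". On the last criterion the text says: "Examples of such events could include allergic bronchospasm, convulsions, and blood dyscrasias". None of the six mentions a CTCAE grade.

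Section 9.3.2 collects adverse events of grade 3 or higher and records seriousness as an attribute of those events. Section 9.3.3 leaves out of the concomitant-medication record any medicine given to treat an event of grade 2 or lower. Section 9.7.2.4 points to Section 11.1 for the definitions of adverse events, serious adverse events and other findings to be collected. Section 9.7.2.5.1 provides, if necessary, for subgroup summaries of all adverse drug reactions and states no grade limit.

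**The concern.** Seriousness and severity grade are different axes. The protocol treats them so: the sample reporting form in Appendix C has one column for the serious criteria and a separate one for severity (mild, moderate, severe). A moderate event with prolonged hospitalization is a valid entry on that form. An exemption cut on one axis removes events that matter on the other, unless it is reversed for every serious criterion. Here it is reversed for one, death.

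The survey is part of the risk management plan, and Section 8 states its general aim as obtaining safety information on long-term use. Infections and neurologic events are among the named risks. If a low-grade event of this kind leads to a hospital stay, the sponsor would reasonably want to know. This is a rule about collection, so no later analysis plan can repair it: events that were never recorded cannot be recovered.

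**Working it through.** The check is a comparison of text. The question is whether any clause brings a non-fatal serious event of grade 2 or lower back into required collection.

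1. **Exemption (11.2).** Defined by grade only, with no condition on seriousness.
2. **Exception (11.2).** Fatal outcome only. If serious events already lay outside the exemption, this sentence would not be needed, since death is itself a serious criterion. Its presence supports the literal reading that other serious low-grade events are exempt.
3. **Residual clause (11.2).** Reaches only information that the section does not specify. Events of grade 2 or lower are specified there, so it does not reach them.
4. **Local-authority sentence (11.2).** If the words about other medicinal products qualify both terms, the sentence covers only exempted events suspected to be due to another product, and one attributed to blinatumomab has no route in it. If they qualify only the second term, every exempted event goes to the authority as local rules require. Neither reading puts the event in the survey data or sends it to the sponsor.
5. **Sections 9.3 and 9.3.2.** Collection is framed at grade 3 or higher. Section 9.3 adds other safety information without defining it, which cannot displace an express exemption.
6. **Section 9.3.3.** Treatment given for a low-grade event is not recorded either, so the event leaves no indirect trace there.
7. **Vendor check (opening of Section 11).** Covers incoming information only.
8. **Pregnancy provisions (11.2.1).** Congenital anomalies and pregnancy complications have their own reporting duty.

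Of the six serious criteria, death is restored by the exception and congenital anomaly is covered by 11.2.1. That leaves 6 − 2 = 4 with no override: threat to life, hospitalization, disability, and other medically important events.

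**Numbers.** The plan's only sample-size statement (Section 9.5) is that 40 subjects give 95% confidence of seeing at least one event with a true incidence of 8%. It reproduces: 1 − 0.92^40 = 0.964. The point does not depend on it.

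The documents give no rate for non-fatal serious events of grade 2 or lower. For orientation only, with an assumed incidence p and n = 40, the expected number of affected patients is 40p and the chance of at least one is 1 − (1 − p)^40:

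| Assumed p | Expected patients | Chance of at least one |
|---|---|---|
| 1% | 0.4 | 0.331 |
| 2% | 0.8 | 0.554 |
| 5% | 2.0 | 0.871 |
| 8% | 3.2 | 0.964 |

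The range runs from probably none to a few patients. It shows what would follow from each assumption and is not an estimate.

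**The case against.** The strongest reply is that grade 3 or higher is a deliberate threshold, applied consistently. It governs the objective, the outcome, the sizing rationale and the primary tabulation, and there is no secondary objective. Section 11.1.2 is a definition and imposes no duty to collect; the duty sits in 11.2, which states its exception openly. No section plans a listing or rate of serious events, and the subgroup summary in 9.7.2.5.1 is conditional. How often a hospitalized event or a convulsion is graded 2 or lower depends on CTCAE version 4.0, which Appendix D cites but does not reproduce.

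Much of this stands, and it rules out several stronger readings that a reader might infer:

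- *That the two sections contradict each other.* A definition followed by an express exception is a mismatch in scope, not a contradiction.
- *That these events are neither collected nor reported.* The text says collection is not required; it does not forbid it, and the local-authority route may apply.
- *That a planned serious-event listing is incomplete.* None is planned.
- *That sites will apply the rule differently.* A cut by grade is a clear line, and the documents do not show that it would be read differently.
- *That the serious-event profile would shift by some 10 to 60%.* Such a range arises from dividing one or two hypothetical missed events by the expected patients with grade 3 or higher infections (40 × 8/36 = 8.9) or neurologic events (40 × 3/36 = 3.3): 1/8.9 = 11% and 2/3.3 = 60%. The numerators are invented and the denominators do not count serious events.

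The reply does not remove the gap. The protocol already accepts that seriousness should override the grade cut, but does so for death alone and gives no reason for stopping there. In Section 9.7.2.4, the words on collection may attach only to the last item in the list. Even so, the cross-reference brings the seriousness definition into the safety analysis, while the collection rule does not follow it.

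**Conclusion.** The point holds as a gap in the collection rule. Followed exactly, Section 11.2 lets non-fatal serious events of grade 2 or lower stay outside the survey data and unreported to the sponsor. The primary endpoint and the sample size are unaffected. What suffers is the survey's capture of serious events and the completeness of any summary labelled as covering all adverse drug reactions.

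No magnitude is claimed, because the documents give no rate. The conclusion assumes only that an event can meet a serious criterion at grade 2 or lower. The separate columns of the Appendix C form allow for this, although its severity scale is mild to severe and not CTCAE grade. This is a cheap improvement and does not threaten the main result.

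**What to change.** - In Section 11.2, limit the exemption to non-serious events of CTCAE grade 2 or lower, and state that any event meeting a criterion in Section 11.1.2 is collected and reported to the sponsor whatever its grade. The separate sentence on fatal outcomes then becomes redundant.
- Reword the local-authority sentence so that it is clear which events the phrase about other medicinal products qualifies.
- Align Sections 9.3 and 9.3.2, and narrow the concomitant-medication exclusion in 9.3.3 so that treatment of a serious low-grade event is recorded.
- Keep the primary endpoint at grade 3 or higher and tabulate serious events of grade 2 or lower separately.
- State in Section 9.7.2.5.1 which events its summary covers. Non-serious low-grade reactions will still be absent after this change, so the word all would remain inaccurate.

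The cost is a few sentences and a small number of additional event forms. The documents do not allow the forms to be counted, but with 40 planned patients the burden should be light. If the sponsor does intend to exempt these events, Section 11.2 should say so and give the reason.
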